Single iv loading infusion of 500 units AZD9773 per kg body weight (maximum 50000 units) in a volume of 250 mL over 30 minutes followed by 100 units AZD9773 per kg body weight in a volume of 100 mL over 30 minutes once every 12 ± 2 hours for up to a maximum of 9 iv maintenance doses (maximum 10000 units each) or until the patient no longer requires haemodynamic or ventilatory support and ICU care and there is no evidence of worsening organ failure (see below for duration of treatment).

Placebo:

Placebo will be saline solution (0.9% sodium chloride) administered as iv infusions in an equivalent volume to the active treatment (in a volume of 250 mL for the loading dose and 100 mL for maintenance doses) with the same regimen and at the same times as noted for Dose arms 1 and 2 or until the patient no longer requires haemodynamic or ventilatory support and ICU care and there is no evidence of worsening organ failure (see below for duration of treatment). The pharmacy at each study centre will supply saline for the study.

Duration of treatment

Up to a maximum of 10 doses (a loading dose followed by up to a maximum of 9 maintenance doses) of AZD9773 will be administered, one dose every 12 ± 2 hours until the patient no longer requires haemodynamic or ventilatory support, no longer requires ICU admission and there is no evidence of worsening organ failure for at least 24 hours. Maximum duration of study drug treatment will be up to approximately 5 days for all patients.

Location of treatment

The initial infusion of study drug will be given to patients in a monitored setting (ie, ICU or emergency department, with a nurse to patient ratio of at least 1:2 and with physiological monitoring [vital signs and cardiac]). Another location in the hospital may be acceptable if it meets these criteria and is approved by the CCC. Subsequent doses will be given to patients in a monitored setting as above.

Timing of treatment

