- j Within 3 hours prior to the first dose (preferably at the same time as the first pre-study drug infusion cytokine blood sample).
- k At screening but may be taken at any time during the study.
- l The baseline physical examination (including lung auscultation and dermal examination) should be done within 4 hours before dose administration.
- m A minimum of a lung auscultation and dermal examination must be performed after each dose. In the event of an infusion reaction (as evidenced by a causal change in BP, skin or lung examination), an additional full physical examination should be performed and changes (skin, lung, physical examination and BP) should be recorded in the eCRF.
- n Physical examination should be done at discharge if discharge is before Day 29.
- o One sample should be collected within 12 hours before dose administration (6 hours for lactate).
- p Record only if available and do not draw these laboratory blood samples if not available or required for other purposes.
- q Collect the sample at the routine collection time closest to 8 a.m.
- r In the event a patient experiences a hypersensitivity reaction, a blood sample for tryptase, IgE and quantitative eosinophil count should be obtained at 20 to 60 minutes post suspected infusion or hypersensitivity reaction and at Day 29.
- s There must be an interval of at least 6 hours between the lactate screening samples and the samples at Day 1. To preserve this minimum 6-hour window, the Day 1 samples may in fact need to be taken on Day 2.
- t ECG should be recorded as follows: baseline (pre-infusion Day 1; Day 1 end of infusion; Day 3 before first dose and end of infusion; Day 5 before first dose and end of infusion; Day 5 ECG 4-6 hrs after last dose; Day 10 at the same time as the PK sample; and Day 29 or at discharge. All ECGs will be obtained in triplicate within approximately 1 to 2 minutes, ensuring that the 3rd reading is prior to infusion start for pre-infusion measurements.
- u Collect only those values closest to 8 a.m.
- v PK blood samples should be taken as described in Section 7.7.1. Note: Some PK samples may need to be taken on the following day depending on the time of first dose administration.
- w Weight will be measured at screening as close as possible to the first dose but within 24 hours before the first dose. If the patient is discharged prior to Day 6, weight should be measured at discharge.

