7.3.6 Physical examinations

Physical examinations will be performed at Baseline and Day 29 (or the discharge visit if prior to Day 29) (Table 1) and reported in the physical examination page of the eCRF. The examination should be based on the following body systems: general appearance, skin, head and neck, lymph node, thyroid, musculoskeletal/extremities, cardiovascular, lungs, abdomen, and neurological. A minimum of a lung auscultation and dermal examination must be performed after each dose. Pulmonary auscultation must be performed by a medically qualified staff member who will listen to the patient's lungs to assess whether there is a change from baseline. A dermal examination will also be performed to assess for infusion reactions such as oedema, urticaria and rash. Additional findings of note will be recorded at this time. In the event of an infusion reaction (as evidenced by a change in BP, skin or lung examination), an additional full physical examination should be performed and changes (skin, lung, physical examination and BP) should be recorded in the eCRF.

Height will be recorded at screening. Weight will be recorded at the timepoints specified in Table 1. Screening weight will be measured as close as possible to the first dose but within 24 hours before the first dose.

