7.3.8 Vital signs, pulse, blood pressure and oximetry

Vital signs and blood oxygen-haemoglobin saturation will be collected at the timepoints specified in [Table 1](#).

Vital signs measured will include: BP (systolic and diastolic), pulse rate (PR), RR, and body temperature (oral, aural or core). The method of measuring body temperature must be recorded in the eCRF. BP, RR and PR will be measured after the patient has been in the supine position for 5 minutes.

The oxygen-haemoglobin saturation of the blood will be assessed using standard pulse oximetry or by arterial blood gas for those patients who have an arterial blood gas obtained.

Abnormal values should not be recorded as AEs unless they result in discontinuation from the study or they fulfil the criteria for an SAE.

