13.3.9.2 Adverse events

AEs will be coded according to MedDRA.

TEAEs (events which were not present at baseline or worsened in severity following the start of treatment) will be presented. AEs occurring prior to the start of treatment will be listed only.

The following summaries will be provided:

- A summary of the number and percentage of patients reporting any TEAE, death, at least one severe TEAE, at least one serious TEAE, at least one TEAE possibly related to study drug, at least one TEAE leading to withdrawal from study drug, at least one infusion reaction (as defined in [Appendix C](#)), at least one hypersensitivity reaction by treatment group
- A summary of the number and percentage of patients reporting a TEAE by treatment group, system organ class (SOC) and preferred term
- A summary of the number and percentage of patients reporting a TEAE by treatment group and preferred term
- A summary of the number and percentage of patients reporting a TEAE by treatment group, intensity, SOC and preferred term. For each patient and each TEAE, the maximum reported intensity recorded will be attributed and used in the by-intensity summaries
- A summary of the number and percentage of patients reporting a TEAE by treatment group, by relationship to study drug, SOC and preferred term. The worst

relationship to study drug (most related to treatment) will be attributed and used in the by-relationship summaries

- A summary of the number and percentage of patients reporting an infusion reaction by treatment group, SOC and preferred term
- A summary of the number and percentage of patients reporting hypersensitivity reactions by treatment group, SOC and preferred term.

The following by-patient listing will be provided:

- A listing of all AEs (including non-treatment-emergent events), by treatment group and including centre, patient identifier, AE (SOC, preferred term, reported term), date of onset, date of resolution, duration, severity, seriousness, action taken, outcome and relationship to study treatment.

13.3.9.3 Deaths, serious adverse events, adverse events leading to withdrawal, and other significant adverse events

The following summaries will be provided:

- A summary of the number and percentage of patients reporting a serious TEAE by treatment group, SOC and preferred term.
- A summary of the number and percentage of patients reporting a TEAE leading to withdrawal from study treatment by treatment group, SOC and preferred term.

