(b) Recommended management in the event of a reaction to drug administration.

- Assess severity: mild, moderate, or severe (see Section IV for details).
- Stop infusion and consider treatment options (see Section V for details).
 - Include: observation, acetaminophen, diphenhydramine, steroids, epinephrine, fluids, albuterol, pressors, airway management and other measures in line with accepted medical practice as deemed necessary by the treating physician eg, iv histamine H2 receptor blockers.
- Monitoring (see Section VI).
- Consider restarting infusion after appropriate management and stabilisation or improvement in symptoms.
- Completion of infusion reaction adverse event (AE) form.

III Post infusion

(a) Monitoring

- A minimum of lung auscultation and dermal examination (eg, for oedema, urticaria, rash) should be done after the infusion is complete. In the event of an infusion of hypersensitivity reaction (as evidenced by a causal change in BP, skin or lung examination), an additional full physical examination should be performed and changes (skin, lung, physical examination and BP) should be recorded in the electronic Case Report Form.

- Laboratory parameter measurements
 - At timepoints according to the study plan (Table 1 of protocol).
 - Serum tryptase, IgE and quantitative eosinophil count, 20 to 60 minutes post suspected infusion or hypersensitivity reaction and repeated on blood draw at Day 29.
- (b) Classifying any infusion reactions
 - Timing
 - Early (onset during infusion or within 1 to 4 hours after infusion).
 - Intermediate (4 to 24 hours after end of infusion).
 - Delayed (onset from 24 hours to 4 weeks after end of infusion).
 - Severity (see Section IV).
 - Type
 - Timing: early, late or intermediate.
 - Hypersensitivity reaction versus infusion reaction.
 - (i) Any adverse reaction, which occurs within the dosing time, is potentially an infusion reaction.
 - (ii) A clinical picture of chills, rigors, fever, myalgia, wheeze, cough dyspnoea, altered vital signs or combination of signs and symptoms consistent with allergic phenomena/infusion reaction. Differentiation will be in immune system activation as evidenced by blood parameters eg, tryptase rise and response to slowing the rate of infusion: this will not affect a true hypersensitivity reaction.
- Investigate relationship of frequency, severity to:
 - History (eg, atopy, asthma, drug allergies).
 - Infusion rate.
 - Infusion concentration.
 - Infusion dose.
 - Infusion number.

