
- Laboratory parameters (eg, total or specific IgE, complement, immune complex, tryptase) to help determine aetiology.
 - Response to treatment.
- (c) Re-treatment (after the full 5-day course, patients should not be re-treated)
- (d) Information to patients
- When the blind is broken, tell a patient whether they had active or placebo. For those who have had active treatment say, “In future if you require any treatment derived from sheep you should inform your physician that you have received sheep derived products as a treatment for sepsis.”

IV Classifying infusion reactions

- (a) Severe; new onset, temporally-related (**any one or more of the following**):
- Hypo/hypertension (eg, systolic BP [SBP] change >40 mmHg; absolute SBP <80 or >180 mmHg).
 - Tachy/bradycardia (eg, heart rate [HR] change >20 beats per minute [bpm] or absolute HR >120 bpm or <60 bpm).
 - Tachy/bradypnoea (eg, respiratory rate [RR] change >10/min).
 - Hyperthermia (eg, temperature >40°C).
 - Evidence of significant angioedema (eg, requiring intubation or treatment) or bronchospasm (eg, associated hypoxia or necessitating change in vent settings or treatment).
- (b) Moderate; new onset, temporally-related (**any one or more of the following**):
- SBP change of 20 to 40 mmHg.
 - HR change of 10 to 20 bpm.
 - RR change of 4 to 10/min.
 - Temperature increase, but <40°C.
 - Evidence of non-clinically significant angioedema or bronchospasm.
 - Rash/urticaria/peripheral oedema requiring treatment.
 - Vomiting requiring treatment.

- Symptoms (eg, pruritis, chills, myalgias, arthralgias) or other effects requiring treatment.
- (c) Mild includes any other new onset, temporally-related symptoms or signs consistent with hypersensitivity reactions such as rash, wheeze or urticaria

V Management of suspected infusion reactions

This section includes but should not be limited to the following measures:

Early and intermediate reactions

- (a) Stop or decrease infusion
 - Stop if severe (see Section IV), progressive (continuing to worsen), refractory (eg, moderate reaction which does not respond to treatment) or at discretion of investigator.
 - For other events, infusion will be stopped or slowed
 - If the infusion is not tolerated and there is no previously tolerated rate the investigator may prolong the infusion time to twice the initially planned infusion time for that timepoint (if warranted the infusion time can be doubled again to increase tolerability).

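### The protocol's AE rules conflict on infusion reactions that show only as vital-sign changes, and the planned reaction summary cites the wrong appendix for its definition

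*Protocol*

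**What the plan says.** Five parts of the Protocol bear on this.

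- **Grading and form (Appendix D).** Section IV grades a reaction on any one or more listed criteria that are new in onset and related in time to the infusion. One of the severe criteria is "Tachy/bradycardia (eg, heart rate [HR] change >20 beats per minute [bpm] or absolute HR >120 bpm or <60 bpm". The moderate list includes an SBP change of 20 to 40 mmHg, an HR change of 10 to 20 bpm and an RR change of 4 to 10/min. Section II(b) lists, among the steps after a reaction, "Completion of infusion reaction adverse event (AE) form".
- **AE rules.** Section 7.3.8: "Abnormal values should not be recorded as AEs unless they result in discontinuation from the study or they fulfil the criteria for an SAE". Section 7.3.3 makes a vital-sign deterioration an AE if it meets an SAE criterion or is the reason for stopping the investigational product. Otherwise the investigator may record it at discretion, together with an unscheduled vital-signs page.
- **Reaction-triggered record.** Table 1 footnote m says that in a reaction "changes (skin, lung, physical examination and BP) should be recorded in the eCRF". Section 7.3.6 repeats this and describes a reaction "as evidenced by a change in BP, skin or lung examination".
- **Scheduled vital signs.** Table 1 footnote u: "Collect only those values closest to 8 a.m". Section 4.1 gives the dosing: "Up to a maximum of 10 doses (a loading dose followed by up to a maximum of 9 maintenance doses) of AZD9773 will be administered", 12 hours apart.
- **Planned summary.** Section 13.3.9.2 counts patients with "at least one infusion reaction (as defined in" Appendix C. It also tabulates infusion reactions by arm, system organ class and preferred term.

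**The concern.** The product is a sheep-derived Fab. Infusion and hypersensitivity reactions have their own appendix, a treatment-discontinuation criterion in 5.4.1 and their own by-arm tables. Those tables use coded terms, so a reaction must be entered as an AE before it can be counted. If one section tells sites to complete an AE form and another tells them not to record the same event as an AE, two sites that both follow the protocol can report differently. The statistical section does not settle the matter, because its definition points to an appendix on shipping samples. The scheduled vital-sign data cannot settle it afterwards either.

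**Working it through.** No sample size, power or event count is involved, so the check compares the passages.

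**Step 1: apply each rule to the same event.** Take a reaction seen only as a vital-sign change, judged new in onset and temporally related.

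| Event | Appendix D | Section 7.3.3 | Section 7.3.8 |
|---|---|---|---|
| Meets an SAE criterion | AE form | AE | AE |
| Non-serious, severe, study drug stopped, patient stays in study | AE form | AE (reason for stopping the drug) | Not an AE |
| Non-serious, moderate, study drug continued | AE form | Investigator discretion | Not an AE |

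The second row follows from three further sections. Section 5.4.1 lists a severe infusion reaction as a reason to stop study treatment. Section 5.4.4 keeps patients who stop the drug in the study. Section 5.4.2 does not list an AE among the specific reasons for leaving the study. The study-discontinuation exception in 7.3.8 will therefore rarely apply, while the treatment-discontinuation exception in 7.3.3 does. The rules agree only in the first row.

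**Step 2: follow the definition reference.** Appendix C is the IATA guidance on labelling and shipping biohazard samples and contains no reaction definition. The classification is in Appendix D, and 7.3.3 itself refers there for it. The Appendix C reference is a plain error.

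**Step 3: compare the reaction-triggered record with the grading criteria.** Appendix D IV grades on SBP, HR, RR and temperature, plus clinical signs. Footnote m and 7.3.6 name BP, skin, lung and physical-examination changes. HR, RR and temperature are not named, either as triggers or as items to record. A reaction graded on HR alone need not leave the value that graded it in that record.

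**Step 4: see whether scheduled data could check the reports.** There is one scheduled set a day against about two infusions a day. In the protocol's example schedule (06:00 and 18:00, each over 30 minutes):

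- The morning infusion ends at 06:30, so 08:00 is 1.5 h after it ends.
- The evening infusion starts at 18:00, so 08:00 is 10 h before it.

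The routine set therefore gives no before-and-after pair. The exception is heart rate: footnote t schedules ECGs before and at the end of an infusion on Days 1, 3 and 5, and 7.3.7 takes HR from each ECG. That covers 3 of up to 10 infusions, with no equivalent for BP, RR or temperature.

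**The case against.** A reader might infer that the eCRF holds nothing but morning values, that reactions are defined by vital signs alone, and that the comparison between arms will be unreliable. The documents do not support this.

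- Footnote u limits only the scheduled set. Footnote m, 7.3.6, the unscheduled pages in 7.3.3 and the reaction form all add data when a reaction is recognised. Appendix D VI asks for vital signs every 2 minutes until stable. The fields of the reaction form are not shown.
- Appendix D III(b) identifies reactions from any adverse reaction during dosing or from a mixed clinical picture. The vital-sign cut-offs belong to the severity grading. Under 7.3.3, accompanying symptoms are AEs in their own right.
- Section 7.3.8 has two exceptions, and 7.3.3 allows discretion, so vital-sign AEs are not barred outright.
- Allocation is central and random (6.2.1) and site staff are blinded (6.3.1), so reporting habits are not linked to arm.

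It is also tempting to put a number on chance threshold crossings. Suppose SDs of change across an infusion of 15 to 20 mmHg, 8 to 10 bpm and 4 to 5/min, independent across signs and infusions. A severe change cut-off is then crossed in 3.2% to 13.0% of infusions. Over 10 infusions that is 1 − (1 − 0.032)^10 = 28% to 1 − (1 − 0.130)^10 = 75% of patients. But the protocol gives none of these SDs, the signs are unlikely to be independent, and the calculation ignores the new-onset and temporal conditions and bedside judgement. It is not evidence of the reaction rate this trial would report.

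All of these objections stand. They narrow the problem mainly to isolated, non-serious reactions shown only by vital signs. They do not remove the conflict between sections or the wrong reference.

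**Conclusion.** The contradiction is real, and the passages must be reconciled. Read literally, 7.3.8 keeps non-serious, vital-sign-only reactions out of the AE data, including severe ones that stop the drug. Appendix D asks for an AE form for the same events. The definition reference in 13.3.9.2 is wrong, and the reaction-triggered record omits three of the four vital signs used for grading.

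The consequence is incomplete or inconsistent capture of these reactions in the by-arm summary, with only partial means of checking a reported grade. How many events are affected cannot be derived, because the documents give no reaction frequency. Bias between arms is not shown: with blinded assessors, under-recording at a similar rate in every arm would tend to shrink a true difference rather than create a false one. The summary is descriptive, so no formal test is at stake. The conclusion assumes that sites apply 7.3.8 as written and that the reaction tables are built from recorded AEs, as their coding by system organ class and preferred term implies.

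**What to change.** Three text changes:

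1. State in 7.3.8 and 7.3.3 that a vital-sign change judged to be an infusion or hypersensitivity reaction under Appendix D is recorded on the infusion-reaction AE form and is exempt from the general rule that abnormal values are not AEs. Reconcile the two sections on whether the exception concerns leaving the study or stopping the drug.
2. Change the reference in 13.3.9.2 from Appendix C to Appendix D.
3. Add HR, RR and temperature to the reaction-triggered record in Table 1 footnote m and section 7.3.6.

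These cost an amendment's wording, a site reminder and, if the reaction page lacks them, three eCRF fields. They concern recording only and leave the grading thresholds, dosing and reaction management unchanged.

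Optionally, transcribe BP, HR, RR and temperature before and at the end of infusion from the monitoring already required, at least for the loading dose, and summarise the change by arm. That would let reported reactions be read against the placebo background. The cost is data entry: 4 signs × 2 times = 8 values for the loading dose, or up to 8 × 10 = 80 per patient if done for every infusion.

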4.2 Rationale for study design, doses and control groups

In a Phase IIb study conducted with D-CytoFab employing a loading dose of 250 units/kg followed by 9 doses of 50 units/kg every 12 hours, there was a significant, prompt and sustained suppression of plasma TNF α during treatment such that TNF α was undetectable in nearly all plasma samples obtained during the entire 5 days of active treatment. Modest and transient rises of TNF α in the treated group occurred in only 2 patients. These 2 patients had the highest baseline TNF α levels of the group, suggesting that dosing was in the optimal region. This dosing regimen was found to significantly improve clinical outcomes for the D-CytoFab-treated group with no adverse safety findings.

In a recently completed Phase IIa study (D0620C00004) conducted with AZD9773, similar effects on plasma TNF α were seen. This particular study was not powered to detect efficacy, but did demonstrate that loading doses of up to 750 units/kg and maintenance doses of up to 250 units/kg every 12 hours were well tolerated in patients with severe sepsis.

In this Phase IIb study, which is powered to detect an effect on the parameter of VFD as a measure of efficacy, both the 250/50 units/kg regimen and the 500/100 units/kg regimen will be evaluated to determine which dose regimen should be employed in further clinical studies to evaluate an effect of AZD9773 on 28-day mortality. Both of these dose regimens were well tolerated in the Phase IIa (D0620C00004) study and the 250 units/kg dose was also well tolerated in the earlier D-CytoFab study. A dose regimen lower than 250/50 units/kg was not included in this Phase IIb study because 250/50 units/kg produced significant clinical benefit with D-CytoFab and there is currently no tolerability concern with the doses chosen for this study. The higher dose will explore the possibility of increased benefit with more TNF α suppression and help define the therapeutic dose-response.

The optimal duration of therapy with an anti-TNF α agent is a balance between intervening to suppress TNF α bursts while not inhibiting the host inflammatory response for too long. A treatment period of 5 days was chosen for the Phase IIb study of D-CytoFab and for the recently completed Phase IIa study (D0620C00004) conducted with AZD9773. In this Phase IIb study the maximum treatment period will also be 5 days.

In the D-CytoFab Phase IIb study, and the AZD9773 Phase IIa study (D0620C00004), nearly all patients receiving study drug treatment had undetectable TNF α during dosing, but within 48 hours after the last dose, mean plasma TNF α levels rose to those comparable to placebo recipients, consistent with the plasma half-life of both D-CytoFab and AZD9773 (18-20 hours in AZD9773 Phase IIa study).

The inclusion of a placebo control will enable an evaluation of efficacy and help to identify drug-related AEs from those due to the disease under study. All patients will receive current standard of care for severe sepsis and/or septic shock in addition to AZD9773 or placebo.

Safety laboratory monitoring will include markers for potential cardiac, coagulation, renal, liver, hypersensitivity and immunological events. The measurement of HASA will be performed to determine if exposure to AZD9773 induces HASA formation. Tryptase is a

protease released by mast cells. It is found in all human mast cells but in few other cells and thus is a good marker of mast cell activation. This may be helpful in the assessment of hypersensitivity or infusion reactions should they occur.

